6.0 Statistical Analysis Plan

We will use descriptive statistics to characterize the study participants and survey data. We will use a one sample t-test to compare the mean SUS score at T1 to the threshold score of 71 indicative of "good" usability. To assess whether there was a significant improvement in the continuous secondary cognitive/behavioral outcomes from baseline to end of study (T0 to T1), we will perform two-sided paired t-tests on the pairwise differences. If any of the distributions of pairwise differences suggest asymmetry or nonnormality, the non-parametric Wilcoxon signed-rank test will be performed in lieu of paired t-tests. We will use the McNemar's test for to compare paired proportions. Our primary outcome will be System Usability Scale (SUS) score at first use (T1).

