5.0 Study Procedures

Setting. The study will be performed at Vanderbilt Primary Care One Hundred Oaks – North and South Clinics located within a large ambulatory care facility in Nashville, TN. An EHR (Epic Systems Corp.) stores all clinical data and patients receive access to their clinical data via an integrated and highly-adopted patient web portal, My Health at Vanderbilt (MHAV), that is accessible on desktops and via a native mobile app for iOS and Android mobile operating systems.

Participants and Recruitment. Potential participants will be identified automatically using VUMC's *Subject Locator* to query the EHR for patients with upcoming clinic appointments who meet the discrete inclusion and exclusion criteria. In addition, VUMC population health and quality improvement initiatives have created a report that identifies established patients with diabetes who receive care at the primary care clinics participating in the study and have current diabetes care gaps (e.g., no diabetes eye exam in the last year). These patients are the target population for study (i.e., Vanderbilt primary care patients with diabetes) and as such these patients are potentially eligible to participate in the study. As with *Subject Locator*, with the permission of the clinic director, these patients would be mailed a recruitment letter describing the study and providing contact information for IRB approved study personnel. With approval of the clinic

director, we will send potentially eligible patients a recruitment letter describing the study and providing them with the contact information for IRB-approved study personnel. If after receiving the letter, a patient is interested in the study, they may contact study personnel to learn more and consider participating in the study. The recruitment letter will include a QR code and URL link to a REDCap site where interested patients can check their eligibility for study, review the consent form, and enroll.

Participants will complete an electronic consent form and enroll online via Research Electronic Data Capture (REDCap™) version 5.0.8. Our target enrollment is 60 participants. In accordance with best practices and to reflect groups with distinct usability needs, we will purposively sample to achieve representation of each of the following characteristics: (a) limited health literacy and (b) age over 65. Some participants may have one or more of these characteristics.

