Patients reporting an outside eye exam will be contacted by study staff and asked to complete an Authorization for Release of Medical Information to VUMC via REDCap. If the patient agrees and signs the release, trained study staff will request the records accordingly. Once the eye exam records are received, trained study staff will review the records to determine if the records document screening for diabetic eye disease (i.e., was the participant's self-report of a diabetes eye exam accurate). If the eye exam records do not indicate screening for diabetes related eye disease (i.e., a diabetes eye exam), KSP will contact the participant by phone with this information and encourage the participant to call their eye doctor to schedule a diabetes eye exam. If the participant prefers, the participant will be invited to schedule a diabetes eye exam at Vanderbilt Eye Institute. If the participant can't be reached by phone, they will be sent a letter with this information. Any outside eye exam records received will be scanned into the participant's VUMC medical record and their primary care physician will be notified.

Data Collection and Outcome Measures. Study participants will complete questionnaires electronically via email using REDCap™ at three time points: enrollment (T_0), after first use of the intervention (T_1), and end of study (T_2). Participants will complete an enrollment questionnaire (T_0) including basic demographic questions, items about computer and internet use, and eHealth literacy. Based on prior experience, we estimate time to completion for each questionnaire to be about 20 minutes. Participants will be compensated \$30 each for completing questionnaires (\$90 total if they complete all three). In addition, participants can receive \$10 for using the intervention for the first time.

The primary outcome measures (**Table 1**) will be: (a) ease of use and satisfaction as assessed by the System Usability Scale at T_1 , (b) system usage data as assessed by user analytics at T_2 , (c) user experience as assessed by 'after first use' and final questionnaires and semi-structured interviews at T_2 . In addition, we will assess pre/post change in the following secondary psychosocial outcomes (**Table 1**) to estimate effect size and standard deviations for power analyses necessary to plan a subsequent randomized controlled trial to be proposed in a subsequent IRB application.

Table 1. Outcome Measures

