Primary Outcomes	Measures	Variable Type	How Collected	Time Point
Usability	System Usability Scale (SUS)	Continuous	Questionnaire	T ₁
User experience	Unique study specific items to assess participants' perspectives on content, acceptance, and features and functionality	Categorical	Questionnaire & Interviews	T ₁ and T ₂
Secondary Outcomes	Measures	Variable Type	How Collected	Time Point
Diabetes self-efficacy	Manage Disease in General Scale of the Chronic Disease Self-Efficacy Scales	Continuous	Questionnaire	T ₀ – T ₂
Understanding of Diabetes Monitoring and Preventative Care	Unique study specific items to assess participants' understanding of recommended diabetes monitoring and preventative care	Continuous	Questionnaire	T ₀ – T ₂
Diabetes distress	Problem Areas in Diabetes Scale (PAID-5)	Continuous	Questionnaire	T ₀ – T ₂
Patient-initiated orders	# of patient-initiated orders for evidence-based diabetes monitoring & preventative services (e.g., A1c)	Continuous	EHR Abstraction, Tableau & Clarity Servers	T ₂
Service completion	# of completed (i.e., care received) patient-initiated orders for evidence-based diabetes monitoring & preventative services (e.g., A1c)	Continuous	EHR Abstraction, Tableau & Clarity Servers	T ₂

T₀ = baseline, T₁ = after first use of the intervention, T₂ = 3-month follow up

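### The paired change tests use only participants with both scores, so the estimated mean change may be biased if T2 response depends on baseline and change varies with baseline (minor; cheap to improve)

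*Combined protocol and SAP*

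**What the plan says.** Section 6.0 tests change in the continuous secondary outcomes as follows: "we will perform two-sided paired t-tests on the pairwise differences". If the differences look asymmetric or non-normal, "the non-parametric Wilcoxon signed-rank test will be performed in lieu of paired t-tests". Both procedures need a score at each time point. Section 6.0 has no missing-data rule: no expected non-response, imputation, likelihood model, sensitivity analysis or comparison of responders with non-responders. No other section supplies one.

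Table 1 lists three questionnaire scales for T0 to T2: diabetes self-efficacy, understanding of diabetes monitoring and preventative care, and diabetes distress. Its footnote defines T2 as "3-month follow up". The other two secondary outcomes, orders initiated and services completed, come from the health record at T2 and have no baseline, so they are not in question here.

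On collection, section 5.0 says "Study participants will complete questionnaires electronically via email". Payment is per questionnaire, with the full amount only for those who complete all three. The stated purpose of the change estimates is "to estimate effect size and standard deviations for power analyses" for a later randomized trial. On size, "Our target enrollment is 60 participants", in a single group.

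The interval is labelled inconsistently. Section 6.0 describes it as "from baseline to end of study (T0 to T1", whereas the list of time points in section 5.0 closes with "and end of study (T_2", and Table 1 agrees with section 5.0.

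**The concern.** T2 is an emailed questionnaire three months after baseline, so some T2 answers will probably be missing. A paired test then describes the T2 responders only. Suppose people who start with worse scores answer less often, and low starters tend to rise more than high starters, as regression to the mean implies. Responders then show a smaller average improvement than the enrolled group would have. If people who start with better scores are the ones who do not answer, the error runs the other way.

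This differs from non-response on the System Usability Scale. That scale is measured only at T1, so a non-responder has no earlier value on it. Here the same scale has already been recorded at T0 for everyone who completed the enrolment questionnaire, and the planned test does not use it.

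At stake are the claim of significant improvement on three secondary scales and the effect sizes passed to the planning of the next trial.

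**Working it through.** **Is there a figure to reproduce?** No. The documents give no alpha, power, effect size, SD, T0-T2 correlation or dropout rate, and 60 is a target without a derivation. Everything below except n = 60 and the choice of test is an assumption.

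**Formula.** Let scores be in baseline SDs with higher meaning better, let b be the slope of T2 on T0, and let response depend on T0 only. Then

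bias of the complete-pairs mean change = (b − 1) × m,

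where m = mean T0 of responders − mean T0 of all enrolled. With equal SDs at T0 and T2, b equals the correlation. Two conditions are needed for bias: m ≠ 0 (response depends on baseline) and b ≠ 1 (expected change varies with baseline).

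**Assumed non-response.** Logistic in T0, with log-odds rising by 0.7 per SD worse baseline (odds about double). Setting 10%, 15% or 25% non-response at the mean baseline gives the following by integration.

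| Overall non-response | Expected pairs of 60 | m | bias, b = 0.4 | bias, b = 0.6 | bias, b = 0.8 |
|---|---|---|---|---|---|
| 12% | 53 | 0.078 | −0.6 × 0.078 = −0.05 | −0.4 × 0.078 = −0.03 | −0.2 × 0.078 = −0.02 |
| 17% | 50 | 0.111 | −0.07 | −0.04 | −0.02 |
| 27% | 44 | 0.173 | −0.10 | −0.07 | −0.03 |

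The range is about 0.02 to 0.10 SD. Separate simulation runs of the worst cell gave 0.10 to 0.11.

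**Simulation check.** n = 60, bivariate normal scores, true change 0.30 SD, 27% non-response, 20,000 runs. The comparator regresses T2 on T0 in completers and averages over all T0 scores, which is the maximum-likelihood estimate.

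| Correlation | Paired bias | All-T0 bias | Paired sampling SD / RMSE | All-T0 sampling SD / RMSE | 95% coverage, paired |
|---|---|---|---|---|---|
| 0.4 | −0.104 | 0.000 | 0.165 / 0.195 | 0.163 / 0.163 | 90% |
| 0.6 | −0.069 | 0.000 | 0.135 / 0.152 | 0.135 / 0.135 | 92% |
| 0.8 | −0.035 | 0.000 | 0.096 / 0.102 | 0.097 / 0.097 | 94% |

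The gain is in bias, not in precision: the sampling SDs are almost equal. At correlation 0.6, the chance of a significant paired test falls from 58% (27% non-response unrelated to baseline) to 39%. With no true change, the two-sided 5% test rejects in about 8% of runs.

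**Harsher dependence.** With log-odds 1 per SD and 30% non-response, the bias is −0.15, −0.10 and −0.05 SD at b = 0.4, 0.6 and 0.8, and coverage falls to 84% at b = 0.4.

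**Where the bias vanishes.** With response unrelated to baseline, bias is 0 at every correlation. With b = 1 and response still depending on baseline at log-odds 1, simulated bias was −0.001 (20% non-response) and −0.002 SD (30%).

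**SD of change.** At 27% non-response, the complete-pairs SD is about 0.88 to 0.89 against a true √(2 × 0.4) = 0.894 at correlation 0.6, and about 1.08 against √(2 × 0.6) = 1.095 at correlation 0.4. That is 1% to 2% low.

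**The case against.** A paired t-test with a signed-rank fallback is a conventional analysis for a 60-person pilot. Nothing in the documents shows that T2 response will depend on baseline, and payment for each questionnaire works against attrition. Even in the 27% setting, a bias of 0.07 or 0.10 SD sits inside 95% interval half-widths of about 0.27 and 0.33 SD. The alternative was simulated under the conditions that suit it, with missingness driven by T0 alone. The later trial needs a between-group difference, so an uncontrolled pre-post change is a limited guide to its effect size whatever the missing-data method.

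Most of this stands, and it is why the point is minor. It does not remove the point. Purposive sampling of people with limited health literacy, with understanding of care as one outcome, makes baseline-related non-response plausible, though that is inference. The plan has no means to detect or handle it, and the remedy costs almost nothing.

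A reader might go further in three ways that the documents do not support:

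- That the estimate is biased whenever response depends on baseline. It is not: the bias is zero if expected change does not vary with baseline.
- That non-responders' T0 scores are thrown away. Section 6.0 also plans descriptive statistics on participants and survey data, so those scores leave only the change test.
- That the SDs handed to the next trial are distorted. The SD of change moves by 1% to 2%.

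**Conclusion.** The point holds in a conditional form. The planned tests are complete-pairs analyses, and nothing elsewhere in the plan deals with missing T2 answers. The mean change for the enrolled group may be biased if T2 response depends on baseline and expected change varies with baseline. A slope below 1 is usual for questionnaire scores, so the second condition is realistic; the first is unknown here.

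The size rests entirely on the assumed non-response rate, its dependence on baseline and the correlation, so the calculated range is an illustration and not a prediction for this study. Expressing it as a share of the true change would add another assumption, since 0.30 SD is not in the documents either.

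The calculations take the interval as T0 to T2, the more probable reading. If T1 were meant, the same reasoning would apply to T1 non-response. Severity is minor: these are secondary outcomes of a single-group pilot, and the primary System Usability Scale analysis at T1 is unaffected.

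**What to change.** 1. First reconcile the T0-to-T1 label in section 6.0 with its own mention of end of study and with Table 1, so that the interval tested is unambiguous.
2. In 6.0, state the missing-data rule and estimate change in self-efficacy, understanding and distress with a likelihood-based repeated-measures model: both time points, unstructured covariance, REML, every participant with a T0 score.
3. Report the mean change with its 95% CI, using a bootstrap interval if residuals are clearly non-normal.
4. Keep the paired t-test or signed-rank test as a supportive analysis.
5. Tabulate T0 scores for T2 responders and non-responders, so that readers can see whether baseline-related non-response occurred.

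The cost is SAP wording and a few lines of code, with no new data. With no missing T2 answers, the model gives the same mean change as the paired t-test. The downside is that it assumes missingness at random given T0. It does not remove bias from non-response that depends on the unseen T2 score, and the report should say so.
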